THE EFFECT OF ADDING HIGH DOSE SIMETHICONE TO A STANDARD POLYETHYLENE GLYCOL PREPARATION ON ADENOMA DETECTION RATE DURING SCREENING COLONOSCOPY: A RANDOMIZED CONTROLLED PILOT TRIAL

ABSTRACT

Screening colonoscopy is a procedure that can effectively prevent colorectal cancer. Adequate mucosal visualization is a critical aspect of this procedure and yet, several factors can interfere with it and consequently result in missed lesions. One of the most commonly encountered factors affecting mucosal visualization is a poor preparation and/or the presence of multiple bubbles at the time of colonoscopy. When a large amount of bubbles is found, simethicone (SIM) is commonly injected through the colonoscopy in order to eliminate them and get a better view of the mucosa. However, this practice has been recently associated with outbreaks of multi-drug resistant bacterial infections, in several endoscopy centers. A few studies have used SIM in conjunction with colon preparation agents (CPA) such as polyethylene glycol (PEG), magnesium citrate, and sodium phosphate, in an attempt to improve the overall quality of the preparation. Unfortunately, these studies have reported conflicting results due to a wide heterogeneity in their methodology and each study has used different CPAs and SIM doses. Furthermore, with the exception of one recently published study from China, no study in western literature has reported an increase in adenoma detection rate (ADR) when SIM is added to a CPA. Given this gap in knowledge, we are planning to conduct a pilot study to determine whether adding a high dose of SIM to a CPA results in a statistically significant difference in ADR.

SPECIFIC AIMS

The study's primary aim is to establish if the ADR improves with the addition of high dose SIM suspension to a polyethylene glycol (PEG) preparation. Secondary aims are to determine if this intervention results in shorter withdrawal times, better colon preparation, less intra procedure use of SIM and a higher polyp detection rate (PDR).

BACKGROUND/SIGNIFICANCE

An adequate bowel preparation is paramount for a screening colonoscopy. Mucosal visualization can be dramatically affected by residual stool, bubbles, bile, intraluminal fluid or debris (1, 2). Any of these features can ultimately lead to missed lesions, prolonged endoscopy duration, and decreased patient tolerance. PEG is one of the most commonly used CPAs. A few studies have reported that the addition of low to medium doses of SIM to lower volume PEG regimens (2L) or other CPAs such as sodium phosphate results in overall better colon preparations based on a standardized bubble scale (BS) and Boston preparation scales (BPS) (3-9). Some of these studies have also reported a trend towards a higher number of polyps detected in the patients who added SIM to their CPA. This finding did not reach statistical significance likely due to the fact that they were neither powered enough nor primarily designed to do so.

It is important however, to understand that SIM is not a CPA. It is an anti-foam medication and its purpose is to decrease the amount of bubbles interfering with visualization, provided that there is no stool present. In clinical practice, it is very common to use it as a flush through the endoscope at the time of the procedure for that purpose. Nevertheless, such use of SIM has been recently associated with the formation of biofilm inside the endoscope's operative channels that is not eliminated by standard disinfecting and reprocessing techniques (10). This biofilm leads to persistent moisture that has been noted as a contributing factor to outbreaks of multi-drug resistant microorganisms in a few high level endoscopy centers (11).

In summary, previous studies have shown a trend towards a better overall preparation, and a higher polyp detection rate when a low to medium dose of SIM is added to a CPA. Therefore, the present pilot study is designed to determine if adding high dose SIM to a regular 4L PEG has the potential to positively impact the ADR, a benchmark quality indicator of screening colonoscopy. Adding a high dose SIM to a CPA could not only result in a higher ADR, but also in a decrease use of SIM through the endoscope at the time of the procedure, reducing the risk of possible life threatening infections for future patients.

The intervention in this study although simple and inexpensive has the potential of making a significant impact in the health of our already underserved population. Our health sciences center is the only academic medical facility performing clinical and basic science research in southwest Texas and we serve a large number of patients, most of which are Hispanic Americans with only limited access to healthcare.

RESEARCH PLAN

Study Design:

This is a single-center, prospective, randomized controlled, observer-blinded study of patients undergoing screening colonoscopy at a tertiary care medical facility.

Primary endpoint

To establish if the ADR improves with the addition of high dose SIM suspension to a polyethylene glycol (PEG) preparation

Secondary endpoints

1. Determine if adding a high dose of SIM to PEG reduces the withdrawal times during the screening colonoscopy.
2. Determine if adding a high dose of SIM to PEG results in an overall better colon preparation.
3. Determine if adding a high dose of SIM to PEG results in less intra-procedural use of SIM.
4. Determine if adding a high dose of SIM to PEG results in a higher polyp detection rate

Inclusion criteria:

1. Patients between the ages of 30-75 scheduled for screening colonoscopy.
2. Male and female patients

3. Ambulatory patients
4. Signed informed consent form
5. Colonoscopy performed by an attending gastroenterologist
6. The use of both Moderate Sedation and Monitored Anesthesia Care (MAC) sedation

Exclusion criteria:

1. Previous colonic surgery
2. Patient with mental/physical condition that impairs oral ingestion of preparation
3. Allergy or hypersensitivity to simethicone
4. Patients with limited mobility (bedridden patients)
5. Patients with gastrointestinal obstruction
6. Patients with GI motility disorders(e.g. achalasia, gastroparesis, chronic constipation)
7. Colonoscopy performed by GI fellows

Patient Enrollment:

Enrollment will be done prospectively until the desired number of patients is reached. This study is planned as a parallel group randomized trial. One group of patients will be randomized to SIM plus PEG while the other group will be randomized to PEG only. The dose of SIM that will be used in this study is 480 mg (2-times higher than the dose used in previous studies). The rationale for using a high dose is to maximize our outcome yield. Our proposed sample size is 300 patients. In our unit, we perform approximately 60 screening colonoscopies per week. We anticipate that approximately 10% of these patients will be eligible to participate in the study. Therefore, we expect to enroll the desired number of patients in approximately 24 months.

Data Collection:

For each patient, the following data will be collected:

1. Age (years)
2. Gender (male/female)
3. Ethnicity (Hispanics/non-Hispanics)
4. Past medical and surgical history (yes/no)
5. Bowel preparation quality (poor, fair, good, very good, excellent)
6. Boston preparation scale score
7. Bubble scale score
8. Cecal intubation time (minutes and seconds)
9. Withdrawal time (minutes and seconds)
10. Effective procedure time (minutes and seconds)
11. Number and size of polyps detected
12. Number of adenomas detected

13. Intra-procedure use of SIM

Sample size calculation

The dose of simethicone that will be used in this study is 480 mg (2-times higher than the dose used in previous studies). The rationale for using a high dose is to maximize our outcome yield. Our sample size calculation was based on articles by Yoo et al⁸, Jansen et al⁹ and Bai et al¹⁰ using the following formula considering ADR as the primary outcome:

$$n = 2 \frac{\left(z_{1-\frac{\alpha}{2}} + z_{1-\beta} \right)^2 pq}{(p_1 - p_2)^2}$$

Where p1 was the % of outcome in the intervention group and p2 the % of outcome in the control group. Bai et al¹⁰ reported ADR of 21.0% in the PEG+SIM group and 14.3% in the PEG group. With these results, a sample size of 509 per group would be suitable for the parent study. For the pilot study, 10% of the calculated sample size for the parent study would be an acceptable estimation¹³. Considering the heterogeneity of the study by Bai et al, we decided to include 20% of the total calculated sample size in this pilot study. Therefore, 102 patients per group would be an appropriate sample size to compare ADR in this pilot study.

Other outcomes to explore in the current study include preparation quality and PDR. Yoo et al⁸ reported that 99% of patients receiving PEG+SIM had BPS scores of 6-9 compared to only 84% in the patients who received PEG. Considering BPS scores as the outcome (p1=99% and q1=84%), with $\alpha=0.05$ and $\beta=0.2$, a total of 110 patients will be needed, 55 in each arm. On the other hand, Jansen et al⁹ reported that PDR in patients who received PEG+SIM was 26.7% compared to 13.7% in those who received PEG. With these results and following the same formula, a sample size of 150 patients per group will be needed to evaluate both bowel preparation and PDR. Therefore, in order to have a sufficient study power and examine all parameters (ADR, PDR and bowel preparation quality), we decided to include 150 patients per group for a total of 300 patients.

Statistical analysis

1. Continuous data (e.g. effective procedure time, withdrawal time) will be described using mean and standard deviation (SD) or Median (Q1, Q3) based on D'Agostino-Pearson normality test in each group and will be compared with either independent t-test or nonparametric Mann-Whitney. Interval data (e.g. BPS, BS) will be presented as Median (Q1, Q3) in each group and compared with nonparametric Mann-Whitney. Categorical data (e.g. ADR) will be described using frequency and proportion (%) in each group and will be compared using Chi-square or Fisher's exact test where appropriate. Further, number needed to treat (NNT) using SIM+PEG will be determined. Cohen's kappa coefficient will be used to measure inter-rater agreement between two endoscopists who will score BS and BPS. In the eventual presence of baseline differences in cofactors, a relative risk regression developed by our biostatistician¹⁴ will be used

to determine adjusted effect of SIM+PEG compared to PEG alone on PDR and ADR. Other findings at colonoscopy

All the statistical analyses will be performed using STATA 14 and p-values less than 5% will be considered significant results. All the statistical analyses will be performed by our Biostatistics and Epidemiology Consulting Lab (BECL) under the supervision of [name].

METHODS

Patients will be included in the study in a prospective manner at University Medical Center of El Paso endoscopy unit. At the time of the pre-op appointment, the assessment nurse will provide all patients with routine instructions for colonoscopy including diet, hydration and fasting. At the same appointment, the research coordinator, and/or an investigator will consent the patients and the research coordinator will randomize them using a random number list generated by a simple block randomization scheme by our study statistician, to one of two possible preparations: PEG+ SIM or PEG alone. The randomization will be via sealed envelopes that will contain cards with the type of preparation to be used. These coded envelopes will be randomly chosen by the patient. Following randomization each patient will be assigned a code corresponding to one of the two preparation regimens. This code will be noted and placed in a master spreadsheet that only the study coordinator and/or assigned research personnel will handle. The simethicone and instructions will be provided to the patients by the research coordinator. Patients randomized to PEG+SIM will drink 2L of PEG at 5 PM the evening before colonoscopy, and 2L 4hrs prior to the colonoscopy. Patients in this group will be instructed to fill a standard 0.6 ml dropper with SIM suspension (40 mg/0.6 ml) a total of 12 times and add it to the gallon of PEG solution. Patients assigned to PEG will drink the preparation in the exact same manner but without SIM.

Prior to the procedure, a safety assessment of each patient will be completed which will include vital signs and a general examination. Patients will also complete a questionnaire evaluating compliance and side effects from the preparation. This questionnaire will be administered and collected by an assigned research team member. The patients will be instructed not to disclose any information regarding the preparation regimen to the endoscopist or any of the procedure nurses.

Colonoscopies will be performed by 4 experienced endoscopists who will be blind to the type of preparation the patient received. All procedures will be performed using Olympus 190 colonoscopes. During colonoscopy, standard parameters such as cecal intubation time, withdrawal time and number of polyps detected will be recorded. For the purpose of this study, withdrawal time will be measured as follows: the timer will be started upon initiation of endoscope withdrawal once the cecum has been reached, and it will be paused every time the endoscopist needs to perform any maneuver or intervention such as polypectomy, biopsy, clip placement, hemostasis, suction for >5 seconds etc. Once the endoscopist is done performing any of these, the timer will be re-started. Endoscopists will be free to ask for SIM during the procedure if he/she deems it necessary and the amount will be recorded by the research coordinator. In addition, endoscopists will be asked to score the preparation according to

the standardized BS (0-3; 3 being the worst) and the BPS (3-0; 3 being the best) . A total BPS score of >6 and a BS of <2 will be considered adequate preparations.

The BS that will be used in this study is the one previously used by Sudduth et al (7). This score grades different sections of the colon as follows: 0 = no or minimal, scattered bubbles believed not to be interfering with the examination; 1 = bubbles covering at least half the luminal diameter; 2 = bubbles covering the circumference of the lumen; 3 = bubbles filling the entire lumen. The overall BS and BPS scores will be determined by adding the scores of each segment of the colon (rectosigmoid, transverse and ascending). For example, in a patient whose individual segment BS scores are as follows: 0,2,1; the final score is 3. All endoscopists will be trained in the use of both scales prior to their participation in the study. The bubble scale and the BPS scores will be independently determined by the endoscopist performing the procedure and by a second endoscopist who will review the still previously selected and labeled by the performing endoscopist and will assign his own score based on these images. Each endoscopist will be blind to the score provided by the other one and inter-observer agreement will be calculated.

The ADR will be calculated once the pathology results of the polyps removed become available.

INNOVATIONS

To the best of our knowledge, this is the first study designed specifically to evaluate the effect of high dose of SIM in conjunction with 4 L PEG preparation on ADR in a western population. Our pilot design will produce rapidly available data that will be then used to design a full sized trial that will definitively confirm or refute our hypothesis, which is that adding SIM to PEG improves ADR. Our study is innovative in its methodology in the following aspects: 1. It is the first one to use a 4 L PEG preparation in both arms (previous studies have used 2 L PEG or other CPAs); 2. It is the first one performed in a standardized average risk western population undergoing screening colonoscopy (previous studies have included both screening and diagnostic colonoscopies); 3. It is a randomized controlled trial and its proposed methodology is a cost-effective approach compared to other alternatives; and 4. Inter-observer agreement of both BPS and BS will be calculated, reducing the potential for bias.

REFERENCES

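### The claim of sufficient power for ADR, PDR and preparation quality at 150 per group is not supported by the plan's own figures: ADR power is about 33%, and the PDR figure uses a control rate below the assumed control ADR

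*Combined protocol and SAP*

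**What the plan says.** All places are in the combined protocol and SAP.

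- **Patient Enrollment** describes two parallel arms: "One group of patients will be randomized to SIM plus PEG while the other group will be randomized to PEG only". There is therefore one PEG-only arm.
- **Sample size calculation, ADR.** One cited study "reported ADR of 21.0% in the PEG+SIM group and 14.3% in the PEG group". The plan derives 509 per group for a later parent study and takes 20% of that, 102 per group, for the pilot.
- **Sample size calculation, other outcomes.** The Boston preparation scale (BPS) needs 55 per group (99% vs 84%). For PDR, a different cited study is used: "PDR in patients who received PEG+SIM was 26.7% compared to 13.7% in those who received PEG". From this, "a sample size of 150 patients per group will be needed to evaluate both bowel preparation and PDR".
- **Sample size calculation, conclusion.** The plan adopts 150 per group, 300 in total, "in order to have a sufficient study power and examine all parameters (ADR, PDR and bowel preparation quality".
- **Methods**, on how adenomas are counted: "The ADR will be calculated once the pathology results of the polyps removed become available".
- **Statistical analysis** names a relative risk regression, if baseline cofactors differ, "to determine adjusted effect of SIM+PEG compared to PEG alone on PDR and ADR".

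**The concern.** The concluding sentence names three outcomes and claims adequate power for all of them. Two of the three do not fit.

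First, ADR is the primary endpoint, and the plan has just calculated that it needs 509 per group. A trial of 150 per group cannot have conventional power for the same difference. The Abstract says the pilot is meant to find out whether the ADR difference is statistically significant, so a reader could take a null result as evidence against the intervention when the design could rarely have shown the effect.

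Second, PDR alone sets the sample size, and its control rate of 13.7% is lower than the control ADR of 14.3%. Adenomas are found by pathology of removed polyps. The plan puts both outcomes through the same two-proportion formula and the same type of regression, so both are treated as proportions of patients. On that reading every patient counted for ADR is also counted for PDR, and PDR cannot be the smaller figure in the same arm. The text does not mention the clash. The Innovations section says the pilot's data will be used to design the full-sized trial, so it matters that the starting assumptions can hold together.

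**Working it through.** **Inputs.** ADR 21.0% vs 14.3%; PDR 26.7% vs 13.7%; BPS 99% vs 84%; 150 per group; two-sided α = 0.05 and β = 0.20. All are from Sample size calculation. The plan states α and β only beside the BPS figure, but they reproduce all three sizes.

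**Step 1: reproduce the plan's sizes.** The formula is n = 2(1.96 + 0.8416)² p̄q̄ / (p1 − p2)², with p̄ the mean of the two rates and (1.96 + 0.8416)² = 7.849.

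| Outcome | p̄q̄ | (p1 − p2)² | n | Plan |
|---|---|---|---|---|
| ADR | 0.1765 × 0.8235 = 0.14535 | 0.067² = 0.004489 | 508.3 → 509 | 509 |
| PDR | 0.202 × 0.798 = 0.16120 | 0.130² = 0.0169 | 149.7 → 150 | 150 |
| BPS | 0.915 × 0.085 = 0.07778 | 0.150² = 0.0225 | 54.3 → 55 | 55 |

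The arithmetic is right. For preparation quality, 150 is well above the 55 required.

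**Step 2: power at 150 per group.** Power = Φ[(d − 1.96·SE₀)/SE₁], with d = p1 − p2, SE₀ = √(2p̄q̄/150) and SE₁ = √((p1q1 + p2q2)/150).

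- ADR, 21.0% vs 14.3%: SE₀ = 0.04402, SE₁ = 0.04385. (0.067 − 0.08628)/0.04385 = −0.44, so power is **33.0%**.
- PDR, 26.7% vs 13.7%: SE₀ = 0.04636, SE₁ = 0.04575. (0.130 − 0.09087)/0.04575 = 0.855, so power is **80.4%**.

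**Step 3: can the rates hold together?** In the SIM arm, PDR 26.7% ≥ ADR 21.0%, which is possible. In the PEG-only arm, PDR 13.7% < ADR 14.3%, which is not. The shortfall is 14.3 − 13.7 = 0.6 points.

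**Step 4: what the clash does to PDR power.** The lowest control PDR compatible with the assumed control ADR is 14.3%. This is a limiting case in which every control patient with a polyp has an adenoma. The result depends on what is carried over from the cited study:

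| Held fixed | SIM-arm PDR | Power at 150 per group | n per group for 80% (plan's formula) |
|---|---|---|---|
| SIM-arm rate | 26.7% | 76.1% | 167 |
| Difference, 13.0 points | 14.3 + 13.0 = 27.3% | 79.5% | 154 |
| Risk ratio, 26.7/13.7 = 1.95 | 14.3 × 1.949 = 27.9% | 82.5% | 142 |

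Above the floor the choice matters more. The documents give no local rate, so these are assumptions: for control PDRs of 20% to 40%, power is about 73% down to 62% if the 13-point difference is kept, and 89% up to 95% if the odds ratio is kept.

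**Step 5: precision at 150 per group.** The 95% half-width is 1.96·SE₁: 1.96 × 0.04385 = 8.6 points for ADR and 1.96 × 0.04575 = 9.0 points for PDR. If the planned ADR rates were observed exactly, the interval would be 6.7 ± 8.6, or −1.9 to 15.3 points.

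**The case against.** The strongest case on the other side has four parts.

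1. *This is a pilot.* ADR was sized at 20% of the parent trial, and 150 exceeds the resulting 102, so the closing sentence may only mean that the pilot fraction is met. That defends the sample size. It does not defend the wording, because a pilot fraction is not power and the sentence says power.

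2. *The rates come from different studies.* The plan attributes each pair to its own source and ties each n to its own pair, so the conditionality is partly visible. Each rate may be true where it was observed. This stands, but the text never says that the two control rates clash when applied to one arm.

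3. *The gap is within sampling error.* The source sizes are not in the documents. If each study had 1,000 control patients (an assumption), each rate would have a standard error of about 1.1 points. Separating 13.7% from 14.3% at the 5% level would take about 1.96² × (0.1182 + 0.1226)/0.006² ≈ 25,700 control patients per study. This stands. The gap is no evidence that either study is wrong.

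4. *PDR is never formally defined.* The per-patient meaning is inferred. It is the meaning that fits the two-proportion formula and the regression, but it remains an inference.

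A reader might infer that the trial is underpowered for PDR, or that 300 is the wrong number. The documents do not support that: at the floor, power falls on both sides of 80%. That a slight rise in the control rate takes power below 80% is no separate fault either, since this is true of any size rounded up to 80% power. Nor is there reason to lower the cited ADR to fit the PDR study.

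**Conclusion.** The power claim is wrong for ADR and only conditional for PDR; for preparation quality it holds on the plan's figures. At the plan's own rates, 150 per group gives about 33% power for the primary comparison. The 80% for PDR holds only at 26.7% vs 13.7%, and that control rate is incompatible with the assumed control ADR.

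Of the two, the ADR part is the larger. The PDR part is an unacknowledged inconsistency of 0.6 points in a secondary endpoint. Its effect at the floor is modest and can go either way (76% to 82.5%).

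The conclusion rests on three assumptions: PDR and ADR are per-patient proportions; α and β are as stated for BPS; and all 300 patients are analysed, since no dropout allowance is given or applied here. The calculations contain no arithmetic error and give no reason to change the number of patients.

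**What to change.** Keep 300 patients, and leave the cited ADR rates and the 509 as they are. Reword the end of Sample size calculation to say that:

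- 150 per group was set by the PDR calculation and gives 80% power conditional on 26.7% vs 13.7%;
- these rates come from a different study from the ADR rates, and the control PDR is not compatible with the assumed control ADR of 14.3%;
- PDR power should therefore be read at a control PDR of at least 14.3%, naming the effect measure held fixed: at 14.3%, 76% (SIM-arm rate kept), 79.5% (difference kept) or 82.5% (risk ratio kept). Any higher control PDR should be labelled as an assumption;
- for ADR, 150 per group gives about 33% power at 21.0% vs 14.3%. ADR should be removed from the claim of sufficient power.

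Add to Statistical analysis that the ADR and PDR differences will be reported with 95% confidence intervals, with an expected half-width of about 9 points.

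The cost is a few sentences and two intervals, with no added patients. The downside is that the stated power looks less favourable.

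### The sample size section justifies 150 per group by adequate power and names ADR, but on the plan's own formula and rates the power for ADR, the primary endpoint, is about 33% and is not stated

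*Combined protocol and SAP*

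**What the plan says.** All of this is in the Research Plan of the combined protocol and SAP, mainly under Sample size calculation.

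- **ADR.** The cited trial "reported ADR of 21.0% in the PEG+SIM group and 14.3% in the PEG group". From these rates the plan concludes that "a sample size of 509 per group would be suitable for the parent study". It then takes 20% of that number for the pilot and says that "102 patients per group would be an appropriate sample size to compare ADR in this pilot study".
- **Bowel preparation.** In a second cited trial, 99% of those given PEG with simethicone "had BPS scores of 6-9 compared to only 84% in the patients who received PEG". The plan derives 55 per arm, with alpha 0.05 and beta 0.2.
- **PDR.** In a third cited trial, the PDR with simethicone "was 26.7% compared to 13.7% in those who received PEG". By the same formula, "a sample size of 150 patients per group will be needed to evaluate both bowel preparation and PDR".
- **Final choice.** The section closes: "in order to have a sufficient study power and examine all parameters (ADR, PDR and bowel preparation quality), we decided to include 150 patients" in each arm, 300 in total.

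Elsewhere, the Primary endpoint section names improvement in ADR. Statistical analysis compares ADR by chi-square or Fisher's exact test at the 5% level and adds a number needed to treat (NNT). The Abstract gives the pilot the aim of finding out whether the ADR difference is statistically significant. The Innovations section leaves the definitive answer to a full-sized trial designed from the pilot's data.

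**The concern.** The closing sentence puts adequate power and ADR side by side without a qualifier, and it follows a calculation in which ADR needed 509 per group. A reader who takes it at face value will believe that the primary comparison is reasonably powered at 150.

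What is at stake is how the result is read. If the assumed effect is real, the primary test will miss it about two times in three. The plan would then report a non-significant ADR comparison beside an NNT, with no interval specified. Readers who had been told that power was adequate could take this as evidence that simethicone does not improve ADR. That would also be a poor basis for the full-sized trial that the pilot is meant to inform.

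**Working it through.** **Inputs.** From Sample size calculation: ADR 0.210 vs 0.143, PDR 0.267 vs 0.137, BPS 6-9 0.99 vs 0.84, equal groups, two-sided formula. Alpha 0.05 and beta 0.2 are printed only beside the bowel preparation calculation. They are assumed for ADR and PDR because they reproduce the stated numbers. The plan makes no dropout allowance, so none is used.

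**Step 1: reproduce the plan's figures.** The formula is n = 2(z₀.₉₇₅ + z₀.₈₀)² p q / (p1 − p2)², with p the mean of the two rates, q = 1 − p, and (1.960 + 0.842)² = 7.849.

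- ADR: 2 × 7.849 × 0.1765 × 0.8235 / 0.067² = 508.3, stated as 509.
- PDR: 2 × 7.849 × 0.202 × 0.798 / 0.13² = 149.7, stated as 150.
- BPS 6-9: 2 × 7.849 × 0.915 × 0.085 / 0.15² = 54.3, stated as 55.

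All three reproduce, so the arithmetic is sound. The final 150 equals the PDR requirement.

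**Step 2: invert the same formula for power.** Power = Φ(|p1 − p2| / √(2pq/n) − 1.960).

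| Outcome | n per group | Power, plan's formula | Exact power, chi-square |
|---|---|---|---|
| ADR | 102 | Φ(1.255 − 1.960) = 24.0% | 23.9% |
| ADR | 150 | Φ(1.522 − 1.960) = 33.1% | 33.2% |
| ADR | 509 | 80.1% | not computed |
| PDR | 150 | Φ(2.804 − 1.960) = 80.1% | 81.0% |
| BPS 6-9 | 150 | 99.7% | over 99.9% |

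With Fisher's exact test, ADR power at 150 per group is 27.7%.

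**Step 3: difference detectable with 80% power from a 14.3% control ADR.** It is 13.1 points at 150 per group and 16.4 points at 102. The plan assumes 21.0 − 14.3 = 6.7 points.

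**Step 4: precision at 150 per group.** The expected 95% half-width for the ADR difference is 1.96 × √[(0.21 × 0.79 + 0.143 × 0.857)/150] = 0.086, or 8.6 points.

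**Step 5: what the trial would show if it observed the assumed effect.** Take 31/150 vs 21/150, a difference of 6.7 points. Chi-square p = 0.13, and the 95% CI is −1.9 to 15.2 points. The NNT is 1/0.0667 = 15. Its limits run from 1/0.152 = 6.6 through no effect to a number needed to harm of 1/0.0187, about 54.

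**Step 6: sensitivity to the control rate (an assumption, not in the documents).** With a control ADR of 25%, power at 150 per group is about 25% for the same 6.7-point difference and about 59% for the same ratio of rates.

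**The case against.** The best defence is that the section can be read coherently. It sets three requirements: 102 per group for ADR as a pilot fraction, 55 for bowel preparation and 150 for PDR. It then takes the largest, which meets all three. The list of outcomes in parentheses may belong only to the verb about examining them, in which case no ADR power is claimed. The sentence just before ties 150 to bowel preparation and PDR and leaves ADR out. The 20% pilot fraction is explicit, the 509 is printed, and the definitive answer is left to a later trial.

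Most of this stands. It means that the plan does not hide where 150 came from, and that a careful reader could infer low ADR power. It does not remove the problem. The sentence giving the final justification still joins adequate power to ADR, the ADR power is never given, and the Abstract still seeks a significant ADR difference.

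A second objection is that 33% depends on one cited trial whose heterogeneity the plan itself flags. This study also uses a higher dose than earlier ones, in a different population. That is fair, and the figure is conditional on those rates. But they are the only ADR rates the plan offers, and neither variant in step 6 reaches 80%.

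A reader might also infer that the trial is too small to be justified and should enrol 509 per group. The documents do not support that: a pilot need not be powered for its parent trial's endpoint, and the plan assigns the 509 to the parent study.

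**Conclusion.** The point holds as a misstatement in the justification of the sample size, not as a fault in the design or the arithmetic. On the plan's own formula and rates, 150 per group (about 29% of 509) gives about 33% power for the primary endpoint, and 102 gives about 24%. Only PDR and the BPS 6-9 proportion reach 80% or more.

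This rests on three assumptions: the cited ADR rates, a two-sided 5% test, and the 80% power target taken for ADR because it returns 509. Any dropout would lower ADR power further. It should be corrected before results are read, because the plan as worded invites a non-significant ADR result to be taken as no effect.

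**What to change.** Keep 300 patients and make four changes.

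1. **Sample size calculation, closing sentence.** Say that 150 per group comes from the PDR calculation (80% power at 26.7% vs 13.7%), that it exceeds the 55 per group calculated for BPS 6-9, and that power for ADR at 21.0% vs 14.3% is about 33%.
2. **Sample size calculation, ADR paragraph.** The pilot-fraction rule is already there. Add that 102 per group is not a size powered to compare ADR.
3. **Statistical analysis.** Beside the NNT, report the ADR difference with its 95% CI, and note the expected half-width of about 8.6 points at 150 per group.
4. **Abstract, Specific Aims and Primary endpoint.** Align the aim with Innovations: the pilot estimates the ADR difference for the full-sized trial, and a non-significant result is not to be read as no effect.

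The cost is wording in a few places and one interval from data already to be collected, with no added patients or visits. The downside is that the stated power for the primary endpoint becomes less favourable. The chance of missing a real effect is unchanged, since the sample size stays the same; what changes is how the result may be interpreted.
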